 4. Normalization by Day 5 of laboratory CSS attributes: ferritin, fibrinogen, AST, ALT, leucopenia, tryglycerides, sCD25 (Secondary outcome)
 5. Normalization or $\geq 75\%$ improvement by Day 10 (120 hours) in each of the following laboratory CSS attributes elevated beyond the normal range at randomization: ferritin, fibrinogen, AST, ALT, leucopenia, thrombocytopenia, d-dimer, CRP, triglycerides, sCD25. (Secondary outcome)
 6. Decreased time to achievement of $\geq 93\%$ oxygen saturation on room air. (Secondary outcome)
 7. No increased prevalence of nosocomial bacterial or fungal or viral infection through the time of hospital discharge. (Secondary outcome)
 8. No failure to develop neutralizing antibody to Covid-19 measured at Day 28. (Secondary outcome)
5. Discharge from hospital without the need for intubation/mechanical ventilation. (Secondary outcome)

Significance

If shown effective, early identification of CSS and repurposing anakinra for its treatment in severe Covid-19 illness will help reduce ICU admissions, improve patient outcomes and enhance survival.

Confirmation of a genetic basis for susceptibility to Covid-19 associated CSS as we identified in H1N1 associated deaths (6) will also facilitate risk stratification and future targeted approaches to Covid-19 disease management.

Design

Recruitment and Enrollment: Thirty patients will be recruited for enrollment; potential subjects will be identified from the registry of Covid-19 patients admitted to the University of Alabama Hospital.

Patient Compensation: Not applicable

Eligibility/Inclusion Criteria:

Inclusion criteria:

1. 18 years old or older
2. Molecular diagnosis of SARS-CoV-2 infection and Covid-19 pneumonia
3. Radiographic imaging consistent with Covid-19 pneumonia
4. Room air oxygen saturation <93%
5. Hyperferritinemia (>700 ng/ml)
6. Any three of the following:
 - a. elevated d-dimer (> 500 ng/ml)
 - b. thrombocytopenia (< 130,000/mm³)
 - c. leucopenia (WBC < 3500/mm³) or lymphopenia (<1000/mm³)
 - d. elevated AST or ALT (> 2X ULN)
 - e. elevated LDH (> 2X ULN)
 - f. CRP > 100 mg/L

Exclusion criteria:

1. Participation in other investigational treatment protocols for Covid-19 infection
2. Culture confirmed active bacterial infection requiring antibiotic therapy
3. On mechanical ventilation
4. Previous known hypersensitivity reaction to anakinra
5. Previous known hypersensitivity reaction to E Coli derived proteins
6. Pregnant or breast-feeding females

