Subjects in the SoC only arm with deterioration of respiratory parameters and CSS markers at 48-96 hours will be transitioned to treatment with anakinra. Patients will stay on anakinra until all CSS markers no longer exceed the thresholds required for enrollment or through Day 5 of anakinra treatment, whichever comes first. Anakinra may be continued after Day 5 of treatment at the discretion of the treating physicians.

Informed Consent:

Identified patients who may be eligible for enrollment will be asked to consider participation in the protocol in the context of the informed consent process whereby the risks and benefits of their participation are discussed with a study investigator. As subjects with CSS/MAS are often severely ill,

those with any suspected altered sensorium will not be enrolled without the assent of a family member who is the designated representative of the patient to assist with their decision whether or not to participate.

Randomization:

Randomization will be assigned by the study coordinator using a computer-based randomization algorithm. The respective PIs will remain blinded to treatment group assignment for all subjects until study completion.

Visit Schedule and Study Procedures

Following obtaining informed consent and 1:1 randomization by computer, study assessments will be as follows:

Day 0:

- Record vital signs, ventilation and oxygen support, heart function, and kidney function/support.
- Blood drawn for these tests:
 - ferritin, CBC with diff, CMP, ESR, CRP, fibrinogen, D-dimer, INR/PT, LDH triglyceride level
 - Cytokine-12 panel, IL-18, CXCL9, sCD25, sCD163, IL-1 β , NK/B/T-cell lymphocytes
 - NK cell function assay
- Blood sample for genetic testing for perforin pathway (genetic traits associated with CSS)

Every effort will be made to procure remdesivir as available under existing PUA for all enrolled subjects.

Following completion of the baseline assessments, dosing of study agent (100 mg anakinra or equal volume saline placebo) will commence every 6 hours by subcutaneous administration.

Day 1-Day 9:

- Record vital signs, ventilation and oxygen support, heart function, and kidney function/support.
- Blood drawn for these tests: ferritin, CBC with diff, CMP, ESR, CRP, fibrinogen, D-dimer, INR/PT, LDH

Day 10:

- Record vital signs, ventilation and oxygen support, heart function, and kidney function/support.
- Blood drawn for these tests:

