 - ferritin, CBC with diff, CMP, ESR, CRP, fibrinogen, D-dimer, INR/PT, LDH, triglyceride level
 - Cytokine-12 panel, IL-18, CXCL9, sCD25, sCD163, and subsets of NK/B/T-cell lymphocytes

If after Day 5 but before Day 10, lab studies show that the levels of ferritin, d-dimer, CRP, LDH, AST, ALT have all returned to normal or improved $\geq 75\%$ from noted Day 0 elevations in these laboratory tests AND the subject has $\geq 93\%$ saturation on room air oxygen, the dose of IP will be decreased to twice daily until Day 10.

All study participants will continue to receive current standard of care treatment for Covid-19 infection. It is understood the standard is evolving and that some treatments that are newly considered standard of care (such as remdesivir) may not be available to enrolled subjects.

Withdrawal of Participant Consent and Discontinuation of Study Drug:

Study participation may be discontinued for any of the following reasons:

- a. Subject decision to withdraw consent for study
- b. Evidence of allergy to administered anakinra
- c. Intolerable adverse event as judged by study investigator and participant
- d. Decision to terminate the study by the investigator and the DSMB due to one or more of the following:
 - Death in any subject in which the cause of death is judged to be probably or definitely related to the study drug by the treating investigator.
 - The occurrence in any subject of a life-threatening SAE whose causal relationship to study drug is judged to be probable or definite by the treating investigator.
 - Two occurrences of Grade 3 or higher toxicities (per NCI CTCAE) that are assessed to be related to the study drug by the investigator.
 - Two occurrences of a clinically significant Grade 3 or higher laboratory abnormality (per NCI CTCAE) assessed to be related to the study drug by the investigator.

If the study drug is discontinued, unless the subject withdraws consent, the subject will be followed for the full treatment/observation period (through Day 60) and all data will be collected as scheduled.

If the study drug is discontinued, unless the subject withdraws consent, the subject will be followed for the full treatment/observation period and all data will be collected as scheduled.

Data Collection:

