The primary efficacy analysis will be conducted on a modified intention-to-treat basis and defined as all patients who underwent randomization and received either anakinra or placebo before intubation/mechanical ventilation or death. Descriptive statistics will be used to characterize participants. Continuous data will be summarized by means and standard deviation (SD) and analyzed by student t tests. Categorical data will be described with frequencies and percentages and compared using Fisher's exact or chi square tests. Cox proportional hazards models will be used to calculate hazard ratio for the association between treatment group and death from any cause or need for mechanical ventilation; due to small sample size control for demographic characteristics, clinical variables and comorbidities will likely not be possible. Calculated 95% confidence interval (CI) and $p < 0.05$ will be considered significant. All analysis will be conducted with SAS v 9.4 (Cary, NC, USA).

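### Day 0 oxygen support can vary widely among 30 patients, yet the planned tests ignore it; one pre-specified stratified analysis would recover precision and limit the harm of a chance imbalance

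*Combined protocol and SAP*

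**What the plan says.** **Entry (Eligibility/Inclusion Criteria).** The respiratory criteria are radiographic pneumonia, "Room air oxygen saturation <93" per cent, and an exclusion for patients "On mechanical ventilation". Ferritin above 700 ng/ml and three of six laboratory features are also needed. There is no lower saturation limit and no cap on oxygen support short of ventilation.

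**Size and allocation (Design; Randomization; Visit Schedule).** "Thirty patients will be recruited for enrollment". Allocation is described as "Randomization will be assigned by the study coordinator using a computer-based randomization algorithm" and, in the visit schedule, "Following obtaining informed consent and 1:1 randomization by computer". Blocks, strata and minimisation are not mentioned either way.

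**Outcomes (Specific Aims).** Two outcomes are labelled primary. One is survival to discharge without ventilation, with no reference to the starting level. The other is no rise in oxygen need at 48 hours, judged against the patient's own baseline.

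**Analysis (Statistical Analysis Plan).** Categorical data are compared by Fisher's exact or chi square tests. A Cox model addresses death or ventilation, with the remark that "due to small sample size control for demographic characteristics, clinical variables and comorbidities will likely not be possible". Ventilation and oxygen support are recorded on Day 0 but have no role in the analysis.

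**Background care (Visit Schedule, after Day 10).** "It is understood the standard is evolving", and remdesivir may not be available to every subject.

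**The concern.** A hypoxaemic patient on no oxygen and one on the highest non-invasive support can both enter. They plausibly have very different chances of being ventilated or dying, whatever the drug does. With about 15 patients per arm, a moderate chance imbalance in starting support is not rare.

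Two remedies are usual: balance the factor at randomisation, or account for it in the analysis. The documents describe neither, although the variable is already collected before the first dose. What is at stake is the reading of one small trial. An unlucky split could look like a drug effect or conceal one, and variation that could be explained stays in the error term.

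**Working it through.** **Inputs from the documents.** N = 30; 1:1 allocation, taken as 15 v 15; Fisher or chi square at p < 0.05, taken as two-sided. The plan gives no power, effect size or event rate for its 30 patients, so there is no figure of its own to reproduce.

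**Assumptions.** 9 or 15 of 30 enter on high support (high-flow or non-invasive). Failure (death or ventilation) is 60% on high and 15% on low support, or 70% and 10%. The treatment odds ratio is 1 or 0.2. At 0.2, 60% becomes (0.6/0.4 × 0.2 = 0.30; 0.30/1.30) 23.1%, and 15% becomes 3.4%; 70% becomes 31.8%, and 10% becomes 2.2%.

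**Step 1: how likely is an imbalance?** With 15 per arm the number of high-support patients in one arm is hypergeometric.
- 15 of 30: P(10 v 5 or worse) = 2 × Σ(k=0..5) C(15,k)·C(15,15−k)/C(30,15) = 0.143. For 9 v 6 or worse it is 0.466; for 11 v 4 or worse, 0.027.
- 9 of 30: P(7 v 2 or worse) = 2 × Σ(k=0..2) C(9,k)·C(21,15−k)/C(30,15) = 0.109.

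**Step 2: what does an imbalance do?** The expected difference with no drug effect is (difference in high-support patients / 15) × (high risk − low risk).
- Both 10 v 5 and 7 v 2 differ by 5 patients: 5/15 × 0.45 = 15 points, or 5/15 × 0.60 = 20 points.
- For 7 v 2 at 60/15%: (7×0.6 + 8×0.15)/15 = 36% against (2×0.6 + 13×0.15)/15 = 21%.

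Exact results given a 10 v 5 split (15 of 30 on high support):

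| | 60/15% | 70/10% |
|---|---|---|
| Null rejection, chi square | 10.3% | 13.1% |
| Null rejection, Fisher | 3.7% | 4.8% |
| Chi square power at OR 0.2, balanced split | 34.1% | 28.0% |
| – anakinra arm draws the 10 | 12.6% | 5.4% |
| – control arm draws the 10 | 63.5% | 68.2% |

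Averaged over all 15:15 allocations, null rejection is 5.0% and 4.7% for chi square and 1.6% for Fisher.

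**Step 3: what does a stratified analysis gain?** The stratified exact test conditions on the number of failures within each support stratum. It refers the anakinra total to the convolution of the two hypergeometric distributions and sums the probabilities of totals no more likely than the one seen. Power at OR 0.2, by full enumeration:

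| High support; risks | Fisher | Stratified exact | Gain (points) | Stratified exact + stratified randomisation | Fisher + stratified randomisation |
|---|---|---|---|---|---|
| 9 of 30; 60/15% | 14.2% | 19.8% | 5.6 | 20.8% | 12.5% |
| 9 of 30; 70/10% | 10.8% | 17.7% | 6.8 | 18.9% | 7.9% |
| 15 of 30; 60/15% | 19.5% | 28.1% | 8.6 | 29.1% | 17.8% |
| 15 of 30; 70/10% | 15.5% | 27.1% | 11.6 | 28.4% | 12.5% |

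Null rejection of the stratified exact test is at most 3.0% in these scenarios. Fisher's is 1.6 to 1.8% without stratified randomisation, so part of the gain is relief from Fisher's conservatism. Against chi square the like-for-like gain is smaller. In simulation with 15 of 30 on high support and unstratified allocation, a Cochran-Mantel-Haenszel test has power 37.2% against 35.4% (60/15%), and 35.6% against 30.4% (70/10%).

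**Step 4: what does stratified randomisation add?** About 1 point beyond the stratified analysis (for example 28.1% to 29.1%). If the unstratified test is kept, it becomes conservative: with 15 of 30 on high support, chi square null rejection falls to 3.0% and 1.6%, and Fisher loses power (last column).

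**The case against.** Several stronger readings are tempting, and the documents do not support them.

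- *The trial's error rate is inflated.* It is not. Step 2 shows near-nominal rejection overall for chi square and well below nominal for Fisher. The problem is distortion given an unlucky split, plus lost precision.
- *Both primary outcomes are equally exposed.* The 48-hour outcome is relative to the patient's own baseline, so starting support is partly built in. A patient near the top of the scale also has few steps left to rise, so even the direction of the association is unclear.
- *The plan rules out blocks or strata.* It is silent. The algorithm may already contain them.
- *Entry takes any respiratory state short of ventilation.* Hypoxaemia on room air and radiographic pneumonia are required. Only the support in use is unrestricted.
- *Changing care biases the comparison.* Concurrent 1:1 randomisation protects against this on average, and remdesivir is to be sought for all subjects.
- *Adjustment is forbidden.* The SAP clause says it is unlikely to be possible, is attached to the Cox model, and covers many variables together. It does not bar a single factor.

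It is also fair to say that baseline support is not the only rival explanation of a difference: the movement of deteriorating control patients to anakinra at 48 to 96 hours is at least as strong. Finally, power is low with or without the change.

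What remains is that a plausibly strong, already recorded predictor has no stated role in either allocation or analysis.

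**Conclusion.** The point holds as a matter of precision and of protection against an unlucky split, and the change is worth making. It does not invalidate the design. It applies chiefly to the survival-without-ventilation outcome; for the 48-hour outcome the benefit is uncertain. Under the stated assumptions a stratified exact test gains about 6 to 12 points of power over Fisher's test at an odds ratio of 0.2 and keeps null rejection below 0.05. Even so, power reaches no more than about 29% in these scenarios. Nearly all of the gain comes from the analysis rather than the randomisation. The support shares, failure risks and odds ratio are all assumptions, because the documents give none. If support predicts failure less strongly, the distortion in Step 2 shrinks in proportion to the risk difference.

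**What to change.** **SAP (the main change).** Replace the clause saying that control will likely not be possible with one pre-specified adjustment:
- for the survival-without-ventilation primary outcome, an exact test stratified by Day 0 oxygen support (none or low-flow v high-flow or non-invasive);
- for death or ventilation, a Cox model stratified by the same factor;
- for the 48-hour outcome, the same stratified test, with a note that the gain there is uncertain.

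**Randomization (optional).** State what the algorithm does. If wished, stratify it by this one factor, using permuted blocks of varying, undisclosed size. Do this only together with the stratified analysis, for the reason in Step 4.

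**Cost.** The analysis change needs a sentence or two and no new data. It may lose slightly if support proves not to be prognostic. Stratified blocks would need a new list, would leave some blocks incomplete at N = 30, and would bring some predictability of assignment at a single site. With 30 patients, one factor is the practical limit.

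### Triglycerides and sCD25 have one scheduled post-baseline draw, Day 10, and the plan does not say what happens to patients discharged earlier, so the Day 10 laboratory comparison may be biased in an unknown direction

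*Combined protocol and SAP*

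**What the plan says.** **Outcomes (Specific Aims).** The Day 10 laboratory outcome asks for normalisation or at least 75% "improvement by Day 10 (120 hours) in each of the following laboratory CSS attributes elevated beyond the normal range at randomization". Ten attributes are listed, ending with "thrombocytopenia, d-dimer, CRP, triglycerides, sCD25". A separate Day 5 outcome reads "Normalization by Day 5 of laboratory CSS attributes: ferritin, fibrinogen, AST, ALT, leucopenia, tryglycerides, sCD25 (Secondary outcome"). Discharge without intubation or mechanical ventilation is also an outcome.

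**Schedule (Visit Schedule and Study Procedures).**
- Day 0 draws "ferritin, CBC with diff, CMP, ESR, CRP, fibrinogen, D-dimer, INR/PT, LDH triglyceride level" and a specialised panel that begins "Cytokine-12 panel, IL-18, CXCL9, sCD25, sCD163, IL-1".
- Days 1 to 9 repeat the routine tests, from ferritin through LDH. Triglycerides and sCD25 are not on that list.
- Day 10 draws "ferritin, CBC with diff, CMP, ESR, CRP, fibrinogen, D-dimer, INR/PT, LDH, triglyceride level" and "Cytokine-12 panel, IL-18, CXCL9, sCD25, sCD163, and subsets of NK/B/T-cell lymphocytes".

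No draw is attached to discharge, and no outpatient Day 10 visit is described.

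**Analysis (Statistical Analysis Plan).** Categorical data are compared by Fisher's exact or chi-square test. There is no rule for missing values, early discharge or death in the laboratory outcomes.

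**The concern.** For ferritin, CRP or the blood counts, an outcome phrased as reached by Day 10 can be met on any earlier day, because those tests are drawn daily. For triglycerides and sCD25 it cannot, because nothing is scheduled between baseline and Day 10. A patient who goes home on Day 7 and is not brought back has no post-baseline value for either marker.

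Discharge happens after randomisation and may differ by arm. If it decides who is measured, the patients with a Day 10 value are no longer the randomised groups, and the observed difference need not estimate the treatment effect. With 30 patients at 1:1, or 15 per arm, a few missing values matter.

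**Working it through.** The plan gives no response rate, discharge rate or length of stay, so there is no figure of its own to reproduce. The counts and rates in steps 3 and 4 are assumptions.

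**1. Scheduled post-baseline draws (from the visit schedule)**

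| Test | By Day 5 | By Day 9 | By Day 10 |
|---|---|---|---|
| Routine tests | 5 | 9 | 10 |
| Triglycerides | 0 | 0 | 1 |
| sCD25 | 0 | 0 | 1 |

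Of the ten attributes in the Day 10 outcome, eight are covered by the daily list (AST and ALT through the metabolic panel) and two are not. Of the seven in the Day 5 outcome, the same two have no scheduled value in any patient, discharged or not.

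**2. Time label.** The Day 10 outcome adds 120 hours in brackets. 10 × 24 = 240 hours, and 120 / 24 = 5 days. The two labels disagree, and at 120 hours neither marker is drawn.

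**3. Effect of losing early leavers, with the truth held fixed.** Assume true response of 10/15 on anakinra and 5/15 on placebo: 66.7% − 33.3% = 33.3 points. Let x responders per arm leave before Day 10 unsampled. With R true responders, the complete-case rate is (R − x)/(15 − x). If missing counts as failure, it is (R − x)/15.

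| Responders leaving (anakinra, placebo) | Complete case | Missing = failure |
|---|---|---|
| 7, 2 | 3/8 − 3/13 = 37.5% − 23.1% = 14.4 points | 3/15 − 3/15 = 0 |
| 4, 3 | 6/11 − 2/12 = 54.5% − 16.7% = 37.9 points | 6/15 − 2/15 = 26.7 points |
| 3, 3 | 7/12 − 2/12 = 58.3% − 16.7% = 41.7 points | 7/15 − 2/15 = 33.3 points |

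The sign changes because the same loss does not cost the arms equally. Three departures lower anakinra from 66.7% to 58.3% (8.3 points) but placebo from 33.3% to 16.7% (16.7 points), since placebo has more non-responders left in its denominator. Only a strongly unequal loss, as in the first row, outweighs this.

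**4. Second check, with rates.** Let d be the share discharged early, and rD and rH the response rates in discharged and remaining patients. The true rate is d·rD + (1 − d)·rH. The complete-case rate is rH, and missing = failure gives (1 − d)·rH. Differences are anakinra minus placebo.

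- *Discharge 60% v 30%, rD 0.90, rH 0.40 in both arms.* True: (0.54 + 0.16) − (0.27 + 0.28) = +0.15. Complete case: 0. Missing = failure: 0.16 − 0.28 = −0.12.
- *Discharge 40% in both arms, rD 0.95, rH 0.60 v 0.30.* True: (0.38 + 0.36) − (0.38 + 0.18) = +0.18. Complete case: +0.30. Missing = failure: 0.36 − 0.18 = +0.18.
- *Discharge 50% v 40%, rD 0.90, rH 0.60 v 0.30.* True: (0.45 + 0.30) − (0.36 + 0.18) = +0.21. Complete case: +0.30. Missing = failure: 0.30 − 0.18 = +0.12.

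The error can shrink, reverse, leave unchanged or inflate the difference, depending on the discharge pattern and on a rule that the plan does not give.

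**The case against.** **Discharged patients may be sampled after all.** Nothing says that sampling stops at discharge. Study agent runs to Day 10 even for patients with recovered laboratory values and adequate saturation on room air, patients who stop study drug are followed through Day 60 with data collected on schedule, and an antibody measurement is planned at Day 28. This stands in part, and the claim must be that such patients *may* have no value. The support is indirect, however. The Day 60 clause concerns stopping the drug, not discharge; the schedule it points to is silent on discharge; and the Day 28 measurement has no listed visit.

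**The direction is not fixed.** A reader might infer that the best responders are the ones lost and that the comparison is therefore biased against the better arm. The documents do not support this. They give no discharge or response rates, and do not show that early leavers respond best on these two markers. The working shows bias either way, including in favour of the better arm when that arm loses more patients (4 v 3).

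**Not every early leaver is unevaluable.** The outcome covers only attributes abnormal at randomisation, and neither marker is an entry criterion. A patient with both normal at baseline can be judged from the daily tests. If the requirement for each attribute is read marker by marker rather than as a composite, the other eight are untouched. Both limits stand. IL-18, CXCL9 and sCD163 are not part of this outcome and add nothing to the point.

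**A discharge draw has a cost.** It gives the marker less time to normalise, which could work against an arm that is discharged sooner. This stands and shapes the fix: the earlier draw should supplement a Day 10 sample that can be obtained, not replace it.

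**Conclusion.** The gap is real but small: two of the ten attributes in one secondary outcome depend on a single Day 10 draw, and the plan does not cover patients who have left hospital or died by then. If discharged patients are not brought back, the missing values depend on an event that treatment may influence. The bias could then be material at 15 per arm: 14 to 42 points against an assumed true 33 under complete-case analysis, and 0 to 33 if missing counts as failure.

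These figures rest on assumed counts in which only responders leave, and they ignore the planned move of deteriorating standard-care patients to anakinra at 48 to 96 hours. They show that the direction cannot be determined, and they are not estimates of the bias to expect.

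Two related findings need no assumption about discharge. The Day 5 outcome has no scheduled value for triglycerides or sCD25 in any patient, and the Day 10 label contradicts its own 120 hours.

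**What to change.** - **Schedule.** Add triglycerides and sCD25 to a blood draw on the day of discharge for anyone leaving before Day 10. Keep the Day 10 draw wherever it can be obtained, and state whether discharged patients are asked to return for it.
- **Analysis.** Use the last available value up to Day 10, count death before Day 10 as non-response, and report the sampling day by arm. State whether the outcome is a composite or is assessed marker by marker.
- **Reconciliation.** Bring the Day 5 outcome and the schedule into line, either by drawing both markers at Day 5 or by removing them from that outcome. Resolve the conflict between Day 10 and 120 hours.

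The cost is schedule and analysis wording, plus two tests at discharge for early leavers. The sampling day will vary, and a discharge value used alone gives less time to normalise. Some bias against an arm discharged sooner can therefore remain, which is why the sampling day should be shown by arm.

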All adverse events that are deemed to be serious and meet the definitions provided in section 6.1.5.2, for serious adverse events will be reported as SAEs.

SAEs

Any AE that results in any of the following outcomes will be considered an SAE, as per outcomes as defined according to Code of Federal Regulations (CFR) Title 21 part 312.32.

- Death
- Life-threatening situation (subject was at risk of death at the time of the event. This does not refer to an event that might have caused death if it was of greater intensity.)
- Prolongation of existing hospitalization
- Persistent or significant disability or incapacity
- Congenital anomaly or birth defect
- Important medical events that may not result in death, be life-threatening, or require hospitalization but may jeopardize the subject and may require medical or surgical intervention to prevent one of the above outcomes (based upon appropriate medical judgment)

A data safety monitoring board (DSB) comprised of three UAB Rheumatologist, a UAB pulmonary and critical care specialist, a UAB specialist in infectious disease, UAB specialist in hematology, and a UAB specialist in nephrology will meet following enrollment of the first 15 subjects or quarterly to review inter-current study outcomes and safety data. The DSB for this study will also review any and all deaths that occur during the study within two weeks of the time of death. If it is the assessment of the DSB that deaths or other SAEs during the course of the study are significantly more prevalent in the anakinra treatment arm or the placebo arm, the study will be prematurely terminated.

Statistical Analysis Plan

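### The SAE list names only prolongation of a hospital stay, so a readmission after discharge counts as an SAE only by judgment or through another criterion, and the DSB comparison may count it inconsistently

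*Combined protocol and SAP*

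**What the plan says.** The SAEs section lists six outcomes that make an adverse event serious, introduced "as per outcomes as defined according to Code of Federal Regulations (CFR) Title 21 part 312.32". The regulation's text is not reproduced. The six are death, a life-threatening situation, "Prolongation of existing hospitalization", disability, congenital anomaly, and a last bullet that begins "Important medical events that may not result in death, be life-threatening, or require hospitalization but may jeopardize the subject". That bullet covers events that may need intervention to avert an outcome listed above it, and it is applied "based upon appropriate medical judgment".

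The sentence just before the list sets the reporting rule: "All adverse events that are deemed to be serious and meet the definitions provided in section 6.1.5.2, for serious adverse events will be reported as" (that is, as SAEs). No section carries the number it cites; I take it to mean this list.

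The paragraph on the DSB provides for early termination if the board assesses that "deaths or other SAEs during the course of the study are significantly more prevalent in the anakinra treatment arm or the placebo arm".

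On follow-up, the section on withdrawal and discontinuation of study drug says that after stopping drug, unless consent is withdrawn, "the subject will be followed for the full treatment/observation period (through Day 60"). The next paragraph repeats the sentence without the day.

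**The concern.** Discharge alive without ventilation is a primary outcome under Specific Aims, so patients are expected to leave hospital while still in the study, and some may come back. Under the list as written, an adverse event that lengthens the first stay is an SAE automatically. The same event leading to a new admission a few days after discharge has no such automatic route.

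This matters because the DSB's termination comparison is framed on deaths and other SAEs. A readmission recorded only as an ordinary adverse event is outside that count. The aim on hospital-acquired infection runs only to discharge, so it does not pick up a later infection either. In a 30-patient trial, a few events classified differently can change how the arms compare.

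**Working it through.** The plan states no figure on this point, so the check is mainly a reading of the text against itself.

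1. **The list against its last bullet.** The last bullet describes "Important medical events that may not result in death, be life-threatening, or require hospitalization". Of the three things it names, death and life-threatening situations each have their own entry above. Hospitalization does not; only prolongation does. The bullet presupposes an entry that is missing. This needs nothing from the cited regulation.

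2. **Routes by which a readmission can be an SAE.**
   - Death, life-threatening situation or disability: yes, if the event reaches that level.
   - Prolongation: no; the earlier stay has ended.
   - Congenital anomaly: not relevant.
   - Important medical event: yes, if judged to jeopardize the subject and to need intervention to avert a listed outcome.

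   A readmission can therefore qualify, but never simply because it is a readmission.

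3. **From the list to the DSB.** Reporting as an SAE requires meeting the list. The termination comparison uses deaths and other SAEs. A readmission that one investigator classifies under the last bullet and another does not will enter that comparison in one case and not in the other.

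4. **The window.** Day 60 appears once, in the paragraph on subjects who stop study drug. The visit schedule ends at Day 10, and the only later assessment named is the Day 28 antibody measurement in Specific Aims. The documents do not say until when SAEs are collected for subjects who complete treatment.

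5. **Scale, for illustration only.** Inputs: 30 patients (Recruitment and Enrollment) and 1:1 allocation (Visit Schedule and Study Procedures), so 30/2 = 15 per arm.
   - One patient: 1/15 = 6.7 points. Two patients: 2/15 = 13.3 points.
   - Assume that a significant imbalance means two-sided Fisher p < 0.05 on subjects with any SAE. The DSB rule states no test or threshold; 0.05 is the level in the Statistical Analysis Plan.
   - 5 vs 0: p = 2 × C(15,5)/C(30,5) = 2 × 3003/142506 = 0.042.
   - 4 vs 0: p = 2 × C(15,4)/C(30,4) = 2 × 1365/27405 = 0.100.
   - By the same test, 7 vs 1 gives p = 0.035 and 6 vs 1 gives p = 0.080.

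   Near the boundary, one patient whose only SAE is an uncounted readmission changes the nominal result. The documents give no expected SAE or readmission rate, so how likely this is cannot be computed.

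**The case against.** A reader might infer that a readmission is not an SAE under this protocol and would be absent from the DSB comparison. The documents do not support that. The last bullet says that qualifying events may not require hospitalization; this is permissive and does not shut out events that do. An infection or relapse serious enough for readmission could often qualify by medical judgment. The lead-in also ties the list to a regulation whose text is not available here, so outright exclusion cannot be established.

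Other safeguards exist. Treatment-emergent adverse events are recorded whether or not serious. The DSB reviews study outcomes and safety data as well as SAEs, and termination rests on its assessment. Separate stopping triggers for related toxicities of Grade 3 or higher do not depend on the SAE label.

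Most of this stands, and it limits the point to inconsistent counting. It does not remove it: judgment case by case is not a uniform criterion, and ordinary adverse events are not part of the termination comparison as worded. The recording safeguard also has a limit. After study termination procedures, an event is recorded only if the investigator considers it clinically significant and related, and the protocol does not say when those procedures fall.

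**Conclusion.** The SAE definition is incomplete on its own terms. A readmission after discharge counts only through another criterion or by judgment, so it could be left out of, or enter unevenly into, the between-arm comparison that can end the study. This is a modest drafting defect, worth correcting because correction is nearly free.

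Its size is unknown. The 6.7 points per patient assumes 15 per arm and would hold for any event in a trial of this size; it is not an estimate of the undercount. It applies only if the readmitted patient has no other SAE and the last bullet is not invoked.

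Two further inferences are not supported. A patient discharged on Day 7 might be said to spend 60 − 7 = 53 of 60 days without an automatic hospitalization criterion, but the discharge day is assumed and the documents state Day 60 only for subjects who stop drug. The undercount might also be thought larger in the arm discharged earlier, or to hide a specific drug harm; the documents give no discharge times or readmission data by which to judge either.

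**What to change.** Reword the bullet to cover inpatient hospitalization (including readmission after discharge) or prolongation of an existing stay. The list then agrees with its own last bullet, and readmissions are counted by the same rule in both arms.

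State one SAE collection window that applies to all subjects, and reconcile the Day 60 text with the visit schedule that ends at Day 10. Without this, the rewording alone would not ensure that readmissions are captured. The documents describe no routine contacts after discharge, so the protocol should also say how such events will come to the investigators' notice within the chosen window.

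The cost is a one-line change to the list, a sentence on the window, and a few more SAE reports.
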